6.2 Efficacy Analysis Methods

Counts and percentages, with their corresponding exact 95% confidence intervals, will be calculated for the binomial endpoints (e.g., ORR, clinical benefit). The confidence intervals based on the group sequential tests performed for each cohort will also be calculated.

Time-to-event variables (OS, PFS and DR) and their set time estimates (i.e., PFS 4/6 and OS 6/12) will be analyzed according to the Kaplan-Meier method.

In the SCLC cohort, the evaluation of the efficacy endpoints evaluated by IA and IRC will be shown and compared. The rate of concordance between both evaluation methods for best response, progression status and progression-free survival will be presented with 2-way frequency tables and measures of agreement.

Waterfall plots will be used to describe the best variation of the sum of target lesions during treatment.

The number of patients recruited in any cohort may differ from that pre-specified according to the sample size assumptions. Therefore, the main efficacy results will be calculated according to the planned cohort sample size and, if any cohort sample size differs at least 10% from the assumptions, a sensitivity analysis using all evaluable patients recruited (adjusting the corresponding boundaries to test the null hypothesis) will be performed.

The patient level response will be calculated by means of statistical programming. In the case of a Partial Response followed by a time point with a tumor size reduction lower than 30% compared to the baseline assessment but an increase in the size of the target lesions not qualifying for disease progression (e.g. increase of sum of target lesions compared with the nadir is lower than 20%) then the response will be considered maintained following RECIST advice((“The definition of SD: a clarification” <http://recist.eortc.org/recist-1-1-2/>).

Example: Baseline evaluation: 38 mm, first evaluation: 26 mm (Tumor Size Reduction from baseline = 31.6% PR), second evaluation: 28 mm (Reduction from baseline = 26.3%, but increase from nadir = 7.7%).

The best overall response will be considered as confirmed PR.

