2.3.1 Evaluation of Target Lesions

Complete Response (CR): Disappearance of all target lesions. Any pathological lymph nodes (whether target or non-target) must have reduction in short axis to < 10 mm.

Partial Response (PR): At least a 30% decrease in the sum of diameters of target lesions, taking as reference the baseline sum diameters.

Progressive Disease (PD): At least a 20% increase in the sum of diameters of target lesions, taking as reference the smallest sum on study (this includes the baseline sum if that is the smallest on study). In addition to the relative increase of 20%, the sum must also demonstrate an absolute increase of at least 5 mm. (Note: the appearance of one or more new lesions is also considered progression).

Stable Disease (SD): Neither sufficient shrinkage to qualify for PR nor sufficient increase to qualify for PD taking as reference the smallest sum diameters while on study.

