2.4 Evaluation of Best Overall Response

The best overall response is the best response recorded from the start of the study treatment until the end of treatment taking into account any requirement for confirmation. On occasion a response may not be documented until after the end of therapy so protocols should be clear if post-treatment assessments are to be considered in determination of best overall response. Protocols must specify how any new therapy introduced before progression will affect best response designation. The patient’s best overall response assignment will depend on the findings of both target and non-target disease and will also take into consideration the appearance of new lesions. Furthermore, depending on the nature of the study and the protocol requirements, it may also require confirmatory measurement (see Section 2.6. Confirmatory Measurement/Duration of Response). Specifically, in non-randomized trials where response is the primary endpoint, confirmation of PR or CR is needed to deem either one the ‘best overall response’. This is described further below.

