2.4.3 Best Overall Response: All Time Points

The best overall response is determined once all the data for the patient is known.

Best Response Determination in Trials Where Confirmation of Complete or Partial Response IS NOT Required:

Best response in these trials is defined as the best response across all time points (for example, a patient who has SD at first assessment, PR at second assessment, and PD on last assessment has a best overall response of PR). When SD is believed to be best

response, it must also meet the protocol specified minimum time from baseline. If the minimum time is not met when SD is otherwise the best time point response, the patient's best response depends on the subsequent assessments. For example, a patient who has SD at first assessment, PD at second and does not meet minimum duration for SD, will have a best response of PD. The same patient lost to follow-up after the first SD assessment would be considered inevaluable.

Best Response Determination in Trials Where Confirmation of Complete or Partial Response IS Required:

Complete or partial responses may be claimed only if the criteria for each are met at a subsequent time point as specified in the protocol (generally four weeks later). In this circumstance, the best overall response can be interpreted as in **Table 3**.

Table 3. Best overall response when confirmation of complete response (CR) and partial response (PR) is required.

Overall response. First time point	Overall response. Subsequent time point	BEST overall response
CR	CR	CR
CR	PR	SD, PD or PR ^a
CR	SD	SD provided minimum criteria for SD duration met, otherwise, PD
CR	PD	SD provided minimum criteria for SD duration met, otherwise, PD
CR	NE	SD provided minimum criteria for SD duration met, otherwise NE
PR	CR	PR
PR	PR	PR
PR	SD	SD
PR	PD	SD provided minimum criteria for SD duration met, otherwise, PD
PR	NE	SD provided minimum criteria for SD duration met, otherwise NE
NE	NE	NE

CR, complete response; NE, inevaluable; PD, progressive disease; PR, partial response; SD, stable disease.

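### SAP 6.2 confirms a partial response on a scan that protocol Appendix 4 classes as stable disease, so the two documents can give different primary responder counts

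*SAP*

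**What the plan says.** **SAP 6.2 (Efficacy Analysis Methods).** Patient-level response is derived by programming. If a PR is followed by a scan less than 30% below baseline that is not progression, "then the response will be considered maintained following RECIST advice". The numeric test offered as an example is that the "increase of sum of target lesions compared with the nadir is lower than 20" per cent. In the worked example (38 mm at baseline, then 26 mm, then 28 mm) no further scan is asked for, and the conclusion is "The best overall response will be considered as confirmed PR". The rule cites a RECIST web clarification on the definition of SD.

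**Protocol Appendix 4.**
- Section 2.3.1 defines PR as "At least a 30% decrease in the sum of diameters of target lesions, taking as reference the baseline sum diameters" and SD as "Neither sufficient shrinkage to qualify for PR nor sufficient increase to qualify for PD", with the smallest sum on study as reference. For PD, besides the 20% rise over nadir, "the sum must also demonstrate an absolute increase of at least 5 mm".
- Section 2.4 says that "in non-randomized trials where response is the primary endpoint, confirmation of PR or CR is needed to deem either one the" best overall response.
- Section 2.4.3 says "Complete or partial responses may be claimed only if the criteria for each are met at a subsequent time point". Its Table 3 lists PR followed by SD as SD.

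**Protocol 7.1** requires confirmation by the same method at least four weeks after the first documentation.

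**SAP 6.1** counts confirmed CR or PR as best overall response in the ORR numerator. The planned ORR sensitivity analyses change the analysis set (SAP 6.1) or the cohort size (SAP 6.2). None changes the confirmation rule.

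**The concern.** Confirmed ORR is the primary endpoint of every cohort, and the final boundaries in protocol 8.1 (at least 2 of 25, 10 of 50, 23 of 100) count confirmed responses. Two operative texts give opposite answers for the same sequence of scans. The difference runs one way: relative to Appendix 4, the SAP rule leaves the count unchanged or raises it. With no analysis that varies the rule, the ORR tables would not show how many responders depend on it.

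The disagreement is narrow. It concerns only patients whose PR is never met again at a later scan at least four weeks after first documentation. PR-SD-PR is not in dispute, because Appendix 4 asks for a subsequent time point and not necessarily the next one. The SAP rule does not cover PR then PD, or PR then not evaluable. The SAP version history shows the rule entering when version 2.0 was updated to version 3, so nothing is implied about interim decisions already taken.

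**Working it through.** **1. The SAP's example (inputs: SAP 6.2).**
- Scan 1: (38 − 26)/38 = 31.6% below baseline.
- Scan 2: (38 − 28)/38 = 26.3% below baseline; (28 − 26)/26 = 7.7% above nadir.

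The SAP's three percentages reproduce.

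**2. The same patient under Appendix 4.**
- PR needs a sum of at most 0.7 × 38 = 26.6 mm.
- PD needs at least 1.2 × 26 = 31.2 mm, a rise of 5.2 mm, so the 5 mm condition is also met there.
- 28 mm meets neither, so scan 2 is SD, and Table 3 gives best response SD.

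In whole millimetres, a second scan of 27 to 31 mm (28.9% to 18.4% below baseline) confirms PR under the SAP and does not under the protocol.

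**3. One patient at each final boundary** (nulls and boundaries from protocol 8.1; exact binomial tail and Clopper-Pearson 95% limit).

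| Cohort | Null | Count | Lower 95% limit | One-sided exact p |
|---|---|---|---|---|
| SCLC | 15% | 22/100 | 14.3% | 0.039 |
| SCLC | 15% | 23/100 | 15.2% | 0.022 |
| Endometrial | 10% | 9/50 | 8.6% | 0.058 |
| Endometrial | 10% | 10/50 | 10.03% | 0.0245 |

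In the 25-patient cohorts the same step is 1/25 to 2/25.

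**4. Chance of reaching the boundary under assumed frequencies.** The documents do not say how often this pattern occurs. Take the protocol-confirmed rate to be exactly at the null, p0, and let a share f of counted responders qualify only through the SAP rule. The counted rate is then p0/(1 − f).
- SCLC: P(X ≥ 23), n = 100.
- Endometrial: P(X ≥ 10), n = 50.
- 25-patient cohorts, with the look at 15: P(X15 ≥ 2) + P(X15 = 1) × P(X10 ≥ 1).

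| Assumption | SCLC | Endometrial | 25-patient cohorts |
|---|---|---|---|
| None affected | 0.022 | 0.025 | 0.022 |
| f = 5% (rates 0.1579, 0.1053, 0.01053) | 0.038 | 0.034 | 0.024 |
| f = 10% (rates 0.1667, 0.1111, 0.01111) | 0.063 | 0.046 | 0.027 |
| 1 percentage point added to p0 | 0.043 | 0.043 | 0.077 |

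The stated one-sided alpha is 0.025. In the last row the implied share of counted responders is 0.01/0.16 = 6%, 0.01/0.11 = 9% and 0.01/0.02 = 50%. The last of these is an extreme case. The SCLC and endometrial figures are for the final count only and ignore the looks at 15 and 25 patients.

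**The case against.** The protocol's standard is RECIST v1.1. Appendix 4 calls itself a summary of it, and protocol 8.2 leaves specific details to the SAP. The SAP states its rule openly, with an example and a source. Because SD takes the smallest sum as reference while PR takes baseline, there may be a real ambiguity that the cited clarification addresses. The source is not in the documents, so which reading of RECIST is better cannot be settled here. That limit stands. It does not remove the conflict: Appendix 4 asks that the PR criteria be met again and tabulates PR then SD as SD, and a SAP that reverses a tabulated outcome does more than add detail.

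The error rates depend on taking p0 as the protocol-confirmed rate. If p0 means the rate under the SAP rule, the SCLC tail stays at 0.022. This is correct; the figures illustrate a choice that the documents leave open.

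The reach is limited. Under the 20% test, a later scan can exceed 70% of baseline only if the nadir is above 0.70/1.20 = 58.3% of baseline. Apart from small sums where the 5 mm condition governs, affected patients therefore have a best shrinkage of roughly 30% to 41.7%. This also stands.

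Three smaller points are fair. The SAP condition refers to progression in general and gives 20% only as an example, so the 5 mm condition may already be included. The SCLC primary analysis uses all treated patients, so its denominator need not be 100. The IRC algorithm is in a charter that is not available here.

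**Conclusion.** The concern holds. SAP 6.2 and protocol Appendix 4 classify a PR followed only by non-progressing scans less than 30% below baseline differently, the difference can only raise the primary responder count, and no planned analysis shows its effect. One patient is enough to decide a cohort that sits at its boundary. Under the assumed 5% to 10% shares, the effect is mainly in the SCLC cohort (0.038 to 0.063) and the endometrial cohort (0.034 to 0.046), and is small in the 25-patient cohorts (0.024 to 0.027). These figures rest on an assumed frequency, which may in fact be zero, and on a protocol-confirmed rate exactly at the null. The finding is that the documents conflict, not that the SAP misreads RECIST. It should be resolved because it concerns the numerator of the primary endpoint.

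**What to change.** Adopt one confirmation rule in both documents, by either route.

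- **Option A: align the SAP with the protocol.** For primary ORR and the boundary counts, require a scan at least four weeks after first documentation, before progression or subsequent therapy, that itself meets the PR or CR criteria. It need not be the next scan, so PR-SD-PR remains a confirmed PR. Report the present SAP rule as a sensitivity analysis.
- **Option B: align the protocol with the SAP.** Amend Appendix 4 to carry the cited clarification, state explicitly whether the 5 mm condition for PD applies, and report ORR and the boundary counts under the present Appendix 4 as a sensitivity analysis.

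Under either option, report the number of affected patients per cohort. Apply the same rule to the investigator and IRC derivations, because SAP 3.3 says the IRC endpoints use the investigator definitions, and check that the IRC charter agrees.

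The cost is one SAP paragraph or one protocol amendment, some programming and one extra ORR table per cohort. No new data are needed: SAP Listings 14.1.23 and 14.1.24 already carry the sums of diameters and the response by cycle. Under Option A the reported ORR may be slightly lower.

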6.2.1 Primary Endpoint

Exact binomial estimates with 95% confidence intervals (CIs) in each cohort will be calculated for the analysis of the main endpoint (ORR according to RECIST v1.1 by Investigator assessment)

6.2.2 Secondary Endpoints

Exact binomial estimates with 95% confidence intervals (CIs) will be performed in the SCLC cohort for the analysis of the ORR according to RECIST v1.1 by IRC.

Time-to-event endpoints (DR, PFS and OS) and their set time estimates (i.e. PFS4, PFS6 and OS 6/12) will be analyzed according to the Kaplan-Meier method.

7 STATISTICAL METHODOLOGY FOR SAFETY

The safety analysis for the secondary endpoints will be based on the “All Treated Patients” population set in each cohort of advanced solid tumors or the total population (if applicable).

Patients will be evaluable for safety if they received any partial or complete infusion of PM01183.

All AEs/laboratory visits reported as “End of treatment” visit will be mapped to the last cycle visit for each patient.

7.1 Toxicity and Adverse Events

All the adverse events will be coded using the Medical Dictionary for Regulatory Activities (MedDRA).

The toxicity evaluation will be coded with the National Cancer Institute Common Terminology Criteria for Adverse Events (NCI-CTCAE) v4.

Treatment-emergent adverse events (TEAE) are defined as any adverse events aggravated in severity from baseline or having their onset between the first dose of the study drug and 30 days after the last treatment dose, death or date of further therapy (whichever comes first). Adverse Events Related to Study Drug or with Unknown relationship occurring more than 30 days after the last dose will also be taken into account as TEAEs.

Summary of overall AEs will be done by System Organ Class (SOC) and Preferred Term (PT), by severity (worst toxicity grade), by relationship to the study drug and by AE outcome. Tables will be

organized by category of events using SOC (i.e. alphabetical order) and PT in descending frequencies (i.e., from higher to lower).

A frequency table or listing will be made for the AEs leading to cycle delay, dose reduction or withdrawal of study medication. Adverse events with outcome of death will also be presented by relationship to the study drugs.

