5.8 EVALUATIONS AT END OF TREATMENT

The *end-of-treatment visit* will be scheduled within 30 days (\pm 7 days) after the last PM01183 infusion, unless the patient starts a subsequent antitumor therapy, in which case the end-of-treatment visit should be performed immediately before the start of the new therapy (ideally the day before or the same day).

Patients, regardless of the reason for ending the treatment, will have to undergo at the end of treatment the following assessments:

- Complete physical examination.
- ECOG PS.
- Vital signs.
- Concomitant therapies.
- Laboratory tests (coagulation panel, hematology and biochemistry A and B).
- Pregnancy test, ECG or LVEF assessment (if clinically indicated).
- Radiological tumor assessment (the evaluation should be repeated at EOT visit, if not previously done, and if the reason for treatment discontinuation is other than PD).
- Adverse events.

These evaluations will only have to be repeated for those parameters for which no measurement is available within 10 days before the EOT visit, or for those parameters with values that were out of range in the last assessment (grade \geq 2 according to the NCI-CTCAE v.4).

Adverse events must be reported for 30 days after the last study treatment administration. All serious adverse events (SAEs) occurring within 30 days of the last study treatment administration or until the start of a new antitumor therapy, whichever occurs first, will be reported. Beyond this period of time, only those suspected to be treatment-related SAEs will be reported (Section [7.7.2](#)).

The Sponsor will evaluate all safety information that is spontaneously reported by an Investigator beyond the time frame specified in the protocol.

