7.7 ADVERSE EVENTS REPORTING PROCEDURES

7.7.1 Reporting Adverse Events

The Sponsor will collect AEs until 30 days after administration of the last dose of the study drug(s)/IMP(s) or until the start of a new antitumor therapy, whichever occurs first. All AEs suspected to be related to the study drug/IMP must be followed-up after the time of therapy discontinuation until the event or its sequelae resolve or stabilize at an acceptable level to the Investigator and the Sponsor.

All AEs, including misuse, overdose and abuse, must be recorded in English using medical terminology in the source document and the CRF. Whenever possible, the Investigator will record the main diagnosis instead of the signs and symptoms normally included in the diagnoses.

Investigators must assess severity (grade) of the event following the NCI-CTCAE v.4 and assign a relationship to each study drug(s)/IMP(s); and pursue and obtain information adequate both to determine the outcome and to assess whether it meets the

criteria for classification as a SAE requiring immediate notification to Pharma Mar or its designated representative. The Investigator must provide any relevant information as requested by the Sponsor in addition to that on the CRF.

Abnormal laboratory tests occurring during the study should only be recorded in the AE section of the CRF if the disorder:

- Is associated with clinically significant symptoms, and/or
- Leads to a change in study dosing or discontinuation from the study, significant additional concomitant drug treatment or other therapy, and/or
- Leads to any of the outcomes included in the definition of a SAE.

Otherwise laboratory results should be reported in the corresponding section of the CRF (i.e., biochemistry, hematology).

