7.7.2 Reporting Serious Adverse Events

The Sponsor will collect SAEs from the time of signing of the informed consent form (ICF) until 30 days after administration of the last dose of study drug(s)/IMP(s) or until the start of a new antitumor therapy, whichever occurs first. Beyond this period of time, only those SAEs suspected to be related to the IMP will be collected. Nonetheless, the Sponsor will evaluate any safety information that is spontaneously reported by an Investigator beyond the time frame specified in the protocol.

All SAEs (as defined above) regardless of relationship to the study drug(s)/IMP(s) must be reported immediately and always within 24 hours to the Pharma Mar S.A. Pharmacovigilance Department as appropriate: electronically (e-CRF), fax ([contact]), e-mail ([contact]) or telephone ([contact]). Out of office hours [Greenwich Meridian Time (GMT)], assistance on SAE reporting can be obtained by calling the Pharmacovigilance Department at [contact]. SAEs initially reported by phone must be followed by a completed electronic SAE reporting on e-CRF from the investigational staff within one working day.

If the SAE occurs after the patient's registration has been confirmed, this information will preferably be reported electronically by completing the applicable eCRF sections.

Those SAEs occurring during the screening phase (from ICF signature to registration) and after off-study will be reported using a paper "SAE form" that must be forwarded as mentioned above and always within 24 hours to the Pharmacovigilance Department.

All SAEs suspected to be related to the IMP(s) must be followed until the event or its sequelae resolves or stabilizes at an acceptable level by the Investigator and the clinical monitor or his/her designated representative.

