8.4 Treatment Administration

Total cumulative dose, dose intensity and relative dose intensity, time on treatment, cycle delays and dose reductions will be described following standard tables detailed in Appendix I.

Total cumulative dose, expressed in mg, will be the sum of all the study drug doses from the first cycle until the last cycle, including the dose received in the last cycle.

Patients will be considered to be on-treatment for the duration of their treatment and for 30 days after the last treatment dose. If the patient starts any new antitumor therapy outside this clinical trial or dies within 30 days of the last treatment dose, the date of administration of this new therapy or the date of death will be considered the date of treatment discontinuation.

However, as a convention, the duration of the last cycle will be considered to be 21 days (instead of 30 days) for dose intensity calculation purposes.

Intended dose intensity is the planned dose per cycle divided by the planned number of weeks per cycle.

Absolute dose intensity is the actual cumulative dose divided by the number of weeks of treatment. Relative dose intensity (%) is the ratio of absolute dose intensity divided by the intended dose intensity.

The CRF item «Infusion delayed: yes/no» will be used to calculate the delayed cycles. For those cycles considered as delayed by the Investigator, the delay will be calculated as follows:

Delay: Date of actual drug administration – Date of previous drug administration – 21.

The infusion of the first cycle will be excluded from all calculations regarding cycle delays and modifications.

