12.2 Adverse Events

12.2.1 Treatment Emergent Adverse Events

Treatment emergent adverse events will be described in this section; treatment-related events (stated as related to the study drug or of unknown relationship) will be tabulated.

Type of toxicity and worst grade or severity by cycle and by patient will be summarized according to the Preferred Term coded with MedDRA. Tables will be organized per category of events using System Organ Class of MedDRA.

Each table, listing and figure displayed in this section will have a comprehensive header identifying the tumor type (cohort) and the total population (if applicable).

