12.2.2 Display of Treatment Emergent Adverse Events

Table 12.2.2.1 Summary of treatment emergent adverse events per patient.

Category**	N	%
Patients with at least one TEAE regardless of relationship		
Any treatment-related** AE		
Any grade ≥3 TEAE		
Any treatment-related grade ≥3 AE		
Any Treatment emergent SAE in DB		
Any treatment-related SAE		
Any grade ≥3 Treatment emergent SAE		
Any treatment-related grade ≥3 SAE		
TEAEs leading to death		
Treatment-related AE leading to death		
TEAEs leading to dose delay***		
TEAEs leading to dose reduction***		
TEAEs leading to treatment discontinuation		
Treatment-related AEs leading to treatment discontinuation		

Note: Also for s1 and s2; (*) Percentage based on number of treated patients; (**) Treatment related adverse event is every event whose relationship is 'Yes' or 'Unknown'. (***) TEAEs leading to dose delay and reduction according to the AE form, with no delay or reduction because the patient discontinues treatment and there is no additional cycle administered are not counted here.

Table 12.2.2.2 Treatment-related adverse events. Worst grade by patient.

Table 12.2.2.3 Treatment-related adverse events. Worst grade by cycle.

Table 12.2.2.4 Treatment emergent adverse events regardless of relationship. Worst grade by patient.

Table 12.2.2.5 Treatment emergent adverse events regardless of relationship. Worst grade by cycle.

Tables 12.2.2.2 to 12.2.2.5 will have the following pattern, but depending on the number and severity of the adverse events observed, the NCI-CTCAE v4 grades may be grouped as ≥1 and ≥3 categories.

SOC	Preferred term	Grade 1		...	Grade 4		Grade ≥1		Grade ≥3
		N	%		N	%	N	%	
Blood and lymphatic system disorders	Anemia NOS			...					
	...								
	...								
Cardiac disorders	Arrhythmia NOS								
	...								

Note: Tables 12.2.2.2 and 12.2.2.4 also for s1 and s2.

Listing 12.2.2.6 Treatment-related grade ≥3 adverse events. Worst grade per patient.

Listing 12.2.2.7 Treatment-related grade ≥3 adverse events. Worst grade by cycle.

Listing 12.2.2.8 Grade ≥3 treatment emergent adverse events regardless of relationship. Worst grade per patient.

Listing 12.2.2.9 Grade ≥3 treatment emergent adverse events regardless of relationship. Worst grade by cycle.

Listings 12.2.2.6 to 12.2.2.9 will have the following pattern:

Patient id.	CTFI**	Cycle*	SOC name	Preferred term	Grade

(*) NA in the per patient summaries; (**) CTFI only for SCLC patients (RR, R, S, VS).

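### SAP 7.1 leaves drug-related adverse events that start after new antitumor therapy but by day 30 outside the TEAE set, although the same events after day 30 are counted

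*SAP*

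**What the plan says.** SAP 7.1 defines a TEAE in two steps. The main window covers events that worsen from baseline or start between the first dose and "30 days after the last treatment dose, death or date of further therapy (whichever comes first"). A second sentence then also admits "Adverse Events Related to Study Drug or with Unknown relationship occurring more than 30 days after the last dose", with no condition on seriousness.

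The protocol's collection rules have a similar shape. Section 7.7.1 collects adverse events "until 30 days after administration of the last dose of the study drug(s)/IMP(s) or until the start of a new antitumor therapy", whichever is first. Section 7.7.2 uses the same end point for serious events (SAEs) and continues: "Beyond this period of time, only those SAEs suspected to be related to the IMP will be collected". Section 5.8 agrees on late related SAEs.

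The plan foresees new therapy inside the 30 days. SAP 8.4 gives a rule for that case: "If the patient starts any new antitumor therapy outside this clinical trial or dies within 30 days of the last treatment dose", the date of that event becomes the date of treatment discontinuation.

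The TEAE definition feeds SAP 12.2. Section 12.2.1 describes TEAEs and states that "treatment-related events (stated as related to the study drug or of unknown relationship) will be tabulated". Table 12.2.2.1, titled as a summary of TEAEs, includes the row "Treatment-related AE leading to death". In SAP 12.3.2, the cause-of-death table (12.3.2.1) has two adverse-event categories, and both are worded as TEAEs.

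**The concern.** The add-back is evidently there so that drug-related events are not lost because the window has closed. It does this only for patients whose window closes at day 30. For a patient whose window closes earlier because new therapy began, the add-back does not start when the window ends. The days in between belong to neither rule.

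The result is the wrong way round. A related event nearer to the last dose of study drug is dropped, while the same event further away is kept. The plan gives no reason for this. What is at stake is the consistency of the safety tables: a related SAE can be in the database and in the SAE outputs but, on a literal reading, outside the TEAE summaries.

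**Working it through.** The plan gives no figure to reproduce, so the check sets the rules side by side. Count days from the last dose and let new therapy start on day t, with t < 30 and the patient alive. Take a related event that starts after treatment began.

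| Onset | In main window (SAP 7.1)? | In add-back (SAP 7.1)? | TEAE? | Systematically collected (Protocol 7.7.1, 7.7.2)? |
|---|---|---|---|---|
| Up to day t | Yes | No | Yes | Serious and non-serious |
| After day t, up to day 30 | No | No | **No** | Related SAEs |
| After day 30 | No | Yes | Yes | Related SAEs |

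The second and third rows have the same collection rule but opposite TEAE status. The arm of the definition for events that worsen from baseline does not close the gap, because it concerns events already present at baseline.

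**Length of the gap.** The main window ends on day t and the add-back begins after day 30, so the gap is 30 − t days:
- t = 14: 30 − 14 = 16 days
- t = 21: 30 − 21 = 9 days
- t = 25: 30 − 25 = 5 days
- t = 29: 30 − 29 = 1 day

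With new therapy on day 21, a related SAE on day 25 is not a TEAE, but the same SAE on day 31 is.

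**Is t < 30 realistic?** Protocol 7.1 schedules scans every two cycles up to Cycle 6, and a cycle is 21 days. The scan therefore falls 2 × 21 = 42 days after the first of the two infusions, which is 42 − 21 = 21 days after the second. If the one-week scan window is taken as plus or minus 7 days, progression would be found on about days 14 to 28 after the last infusion. A switch before day 30 is therefore plausible.

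**How many patients?** The documents do not say. As an assumption only, take 5%, 10% or 20% of 350, the maximum number of evaluable patients:
- 350 × 0.05 = 17.5, about 18 patients
- 350 × 0.10 = 35 patients
- 350 × 0.20 = 70 patients

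At 1 to 16 days each, the total time in the gap runs from 18 × 1 = 18 to 70 × 16 = 1,120 patient-days. The width of that range shows how little is known. Few new related events would be expected in that time: Protocol 1.10.1.3 puts the usual nadir in the second week of the cycle in the first-in-human study.

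**The case against.** The strongest reply is that nothing is hidden. SAP 7.1 itself provides for fatal adverse events to be shown by relationship, with no TEAE condition. Listing 12.3.2.2 gives every death with its cause, and Listing 12.3.2.3 gives fatal events with relationship and onset date. The SAE tables and listings in SAP 12.3.1 are not titled as TEAE-only, and SAP section 14 provides full event and death listings. All of this stands: a related SAE in the gap remains visible. It does not explain why the summaries should classify it differently from the same event a few days later.

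A second reply is that the footnote to Table 12.2.2.1 defines a treatment-related event by relationship alone, so the related rows might include the event anyway. That is a fair reading of the footnote. The table title and SAP 12.2.1 point the other way, and the add-back would be unnecessary if related events counted regardless of timing. The text is ambiguous at best.

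A third reply defends counting related events of any seriousness after day 30, although the protocol then asks only for related SAEs. The rule is inclusive, and Protocol 5.8 and 7.7.2 say that the sponsor will evaluate unsolicited late reports. This also stands. It calls for a footnote on what was systematically collected, not for a narrower definition.

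**Conclusion.** The gap is real on the current wording and follows from the text alone. It applies only to patients who start new therapy before day 30, and its practical content is mainly related SAEs. A literal programmer could leave such an event out of the SAP 12.2.2 summaries. A fatal one would not fit the drug-related TEAE category of Table 12.3.2.1. Summaries and listings could then disagree. Severity is minor: events should be rare, the number of patients is unknown, and the primary endpoint is not involved.

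A reader might infer three stronger things that the documents do not support.

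- *A cohort stopped for two related deaths would report only one.* No section says that the cause-of-death category is derived from a TEAE flag. The planned listing of the death report form (14.1.27) includes a cause, and the related-death row of Table 12.2.2.1 is ambiguous, as noted above.
- *The stopping rule is weakened.* Protocol section 3 counts treatment-related deaths with no TEAE condition.
- *The protocol contradicts itself on when collection ends.* Section 5.8 does say "Adverse events must be reported for 30 days after the last study treatment administration", with no cut-off at new therapy in that sentence. However, the definition of the on-treatment period under the table in Protocol 5.7, together with 7.5 and 7.7.1, stops at new therapy. So does the next sentence of 5.8, for SAEs. The matter is largely settled.

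**What to change.** In SAP 7.1, change the trigger of the add-back from day 30 to the end of the window, for example: *related or unknown-relationship events with onset after the end of this window are also TEAEs*. Keep events of any seriousness. Add a footnote to the TEAE tables stating that, after the window, only related SAEs are systematically collected (Protocol 5.8 and 7.7.2).

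Restricting the add-back to serious events would be a poorer repair. Any non-serious related event recorded in the gap would stay outside the TEAE set, and late non-serious related events that the SAP now tabulates would drop out of the tables.

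The cost is one phrase and one footnote, with no protocol amendment, no extra visits and no new data. The downside is that a few more related events enter the TEAE tables, some with onset under another therapy. That is already true of the events after day 30 that the SAP admits.
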